7.2 Primary outcome variable

7.2.1 Human milk total thiamine concentration (24 weeks)

Outcome:	Continuous outcome of total thiamine concentration ($\mu\text{g/L}$) in maternal human milk at 24 weeks postpartum.
Analysis:	Fit an Emax curve using nonlinear least squares approach. Estimate of the dose that reaches 90% concentration (with 95% CI) will be reported.

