The full statistical analysis plan can be found in **Appendix B**. The primary analyses will be performed on an ‘intention to treat’ basis, where all participants will be analyzed according to their allocated treatment group regardless of compliance. A secondary ‘per-protocol’ analysis will be performed on the subset of women who consumed $\geq 80\%$ capsules over the study period. The parameters of the Emax dose-response curves will be estimated using non-linear least squares models. Separate curves will be fitted for outcomes measured at 4 weeks, 12 weeks, and 24 weeks postpartum. The dose where additional maternal intake of thiamine no longer meaningfully increases milk thiamine concentration, defined as the dose that achieves 90% of the maximum concentration, will be estimated from the fitted curve with standard errors estimated by bootstrapping for calculating 95% confidence intervals.

Comparisons between treatment groups will be performed using linear mixed-effects models to account for repeated measurements and adjusted for randomization strata and levels at 2 weeks postnatal. Interaction tests will be performed to assess whether treatment effects depend on genetic hemoglobin disorder. Missing data will be addressed using multiple imputation to create 100 complete datasets for analysis, with a sensitivity analysis performed on the raw (unimputed) data (68). All analyses will follow a pre-specified statistical analysis plan (see **Appendix B**).

12. Administrative Aspects, and Data Security and Management

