5.3 Methods for withdrawals, missing data and outliers

All available data collected up until time of withdrawal will be included in the statistical analysis.

Multiple imputation using chained equations will be performed separately by randomised treatment group to address missing data under a missing at random assumption. A total of 100 imputations will be performed to ensure $<1\%$ loss of power compared to full information maximum likelihood^[3]. Covariates pre-specified for adjustment in the analysis will be included in the imputation model, along with other auxiliary variables useful for improving the prediction of missing values. Conclusions will be based on the results obtained using imputed data, with sensitivity analyses performed on unimputed data.

Outliers will not be excluded from the primary analysis unless a data entry error is confirmed.

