5.6 Covariates for adjustment

Both unadjusted and adjusted analyses will be performed for some outcomes. Conclusions for these outcomes will be drawn from the adjusted analyses, with unadjusted analyses performed for completeness and to potentially confirm the results of the adjusted analyses.

All adjusted analyses will be adjusted for health centre, since it was used as a stratification variable in the randomisation process. Adjustment will also be made for additional variables collected at 2 weeks postnatal which are potential confounders for some outcomes and these have been identified a priori (see Section 7).

If convergence is an issue, some potential confounders may be excluded from the adjusted analysis. Any deviation from the planned adjustment covariates will be documented in the final report.

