7.1 Emax curve

Analysis of the primary and several secondary outcomes will be based on the Emax curve.

The Emax curve is defined as:

$$Y = E_0 + E_{\max} \left(\frac{\text{dose}^h}{ED_{50}^h + \text{dose}^h} \right)$$

where E_0 is the baseline concentration without supplementation, E_{\max} is the maximum effect of supplementation, ED_{50} is the dose that produces half of the maximum effect of supplementation and corresponds to the inflection point at which the effectiveness of higher doses starts to decrease, and h is the slope or Hill factor.

The nonlinear Least squares model for the primary outcome will be formulated as:

$$Y = E_0 + E_{\max} \frac{\text{dose}^h}{ED_{50}^h + \text{dose}^h} + \epsilon$$

For secondary outcomes involving testing for effect modification by presence or absence of genetic hemoglobin disorder (GD), additional coefficients (α , β , γ and δ) will be added to all parameters of the Emax curve. The model will be formulated as:

$$Y = (E_0 + E_0\beta\text{GD}) + (E_{\max} + E_{\max}\gamma\text{GD}) \frac{\text{dose}^{(h+h\delta\text{GD})}}{(ED_{50} + ED_{50}\alpha\text{GD})^{(h+h\delta\text{GD})} + \text{dose}^{(h+h\delta\text{GD})}} + \epsilon$$

Evidence of curve shape differences between presence or absence of genetic hemoglobin disorder will be determined by global Likelihood ratio tests. Further testing of the four additional coefficients, in the form of H_0 : coefficient = 0, will be conducted following evidence ($P < 0.05$) from the global test.

The parameter of interest for this study is the dose required to achieve 90% of the maximum concentration (i.e. 90% of $E_0 + E_{\max}$) and this will be estimated from the fitted Emax curve with variance estimated from non-parametric bootstrapping of 100 resamples. For outcomes where there is evidence of curve difference by genetic hemoglobin disorder status ($P < 0.05$ for likelihood ratio test), separate estimates for the dose required to achieve 90% of the maximum concentration with and without genetic hemoglobin disorder will be reported.

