7.3 Secondary outcome variables

7.3.1 Infant thiamine diphosphate concentration (24 weeks)

Outcome:	Continuous outcome of infant thiamine diphosphate concentration (ThDP; nmol/L) at 24 weeks postpartum.
Primary analysis:	Fit an Emax curve using nonlinear least squares approach. Estimate of the dose that reaches 90% concentration (with 95% CI) will be reported.
Secondary analysis:	Fit an Emax curve using nonlinear least squares approach allowing curve to vary by presence/absence of genetic hemoglobin disorder. Estimates of the dose that reaches 90% concentration by genetic hemoglobin disorder status will be reported following evidence from the global test. Second, test for a linear relationship using linear regression with CRP at 24 weeks and treatment group as predictors. Estimate of the mean change (with 95% CI) in ThDP for one unit increase in CRP will be reported. Third, test for a linear relationship using linear regression with AGP at 24 weeks and treatment group as predictors. Estimate of the mean change (with 95% CI) in ThDP for one unit increase in AGP will be reported.
Adjustment:	Health centre (linear regressions only)

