7.3.2 Human milk total thiamine concentration (4 weeks and 12 weeks)

Outcome:	Continuous outcome of total thiamine concentration ($\mu\text{g/L}$) in maternal human milk at 4 weeks and 12 weeks postpartum.
Primary analysis:	Fit a separate Emax curve for 4 and 12 weeks using nonlinear least squares model. Estimate of the dose that reaches 90% concentration (with 95% CI) at each timepoint will be reported.
Secondary analysis:	Fit a linear mixed effects model to outcome at 4, 12, and 24 weeks with treatment group, time, and treatment by time interaction as predictors. Treatment effects (difference in mean total concentration) will be estimated separately for each time point if the interaction p-value is <0.05 and for both time points combined otherwise.
Adjustment:	Health centre, human milk total thiamine at 2 weeks postnatal (linear mixed effects model only)

7.3.3 *Infant transketolase activity coefficient (24 weeks)*

- Outcome: Continuous outcome of infant transketolase coefficient (TKac) at 24 weeks postpartum.
- Primary analysis: Fit an Emax curve using nonlinear least squares approach. Estimate of the dose that reaches 90% concentration (with 95% CI) will be reported.
- Secondary analysis: Fit an Emax curve using nonlinear least squares approach allowing curve to vary by presence/absence of genetic hemoglobin disorder. Estimates of the dose that reaches 90% concentration by genetic hemoglobin disorder status will be reported following evidence from the global test.

7.3.4 *Maternal thiamine diphosphate concentration (24 weeks)*

- Outcome: Continuous outcome of maternal thiamine diphosphate concentration (ThDP; nmol/L) at 24 weeks postpartum.
- Primary analysis: Fit an Emax curve using nonlinear least squares approach. Estimate of the dose that reaches 90% concentration (with 95% CI) will be reported.

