- Secondary analyses: First, fit an Emax curve using nonlinear least squares approach allowing curve to vary by presence/absence of genetic hemoglobin disorder. Estimates of the dose that reaches 90% concentration by genetic hemoglobin disorder status will be reported following evidence from the global test. Second, test for a treatment effect using linear regression and estimate a difference in mean concentration. Third, test for a treatment effect using linear regression with treatment group and treatment by genetic hemoglobin disorder interaction. Treatment effects (difference in mean concentration) will be estimated separately by genetic hemoglobin disorder where the relevant interaction term has a p-value <0.05. Pairwise comparisons will be reported following evidence of a treatment group effect (see Section 5.8). Fourth, test for a linear relationship using linear mixed effects model with CRP at 2 and 24 weeks postnatal, time and treatment group as predictors. Estimate of the mean change (with 95% CI) in ThDP for one unit increase in CRP will be reported. Fifth, test for a linear relationship using linear mixed effects model with AGP at 2 and 24 weeks postpartum, time and treatment group as predictors. Estimate of the mean change (with 95% CI) in ThDP for one unit increase in AGP will be reported.
- Adjustment: Maternal ThDP at 2 weeks postpartum, health centre (linear regressions and mixed effects models only)

7.3.5 *Maternal transketolase activity coefficient (24 weeks)*

- Outcome: Continuous outcome of maternal TKac at 24 weeks postpartum.
- Primary analysis: Fit an Emax curve using nonlinear least squares approach. Estimate of the dose that reaches 90% concentration (with 95% CI) will be reported.

- Secondary analyses: First, fit an Emax curve using nonlinear least squares approach allowing curve to vary by presence/absence of genetic hemoglobin disorder. Estimates of the dose that reaches 90% concentration by genetic hemoglobin disorder status will be reported following evidence from the global test. Second, test for a treatment effect using linear regression and estimate a difference in mean TKac. Third, test for a treatment effect using linear regression with treatment group and treatment by genetic hemoglobin disorder interaction. Treatment effects (difference in mean TKac) will be estimated separately by genetic hemoglobin disorder where the relevant interaction term has a p-value <0.05.

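### The primary Emax fit uses dose alone, although the SAP adjusts the same 24-week milk outcome for 2-week milk thiamine elsewhere; the primary dose interval may be wider than it needs to be

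*Combined protocol and SAP*

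**What the plan says.** SAP 7.1 introduces the primary model with "The nonlinear Least squares model for the primary outcome will be formulated as" and gives an equation in E0, Emax, ED50, the Hill factor h and an error term. Dose is the only predictor. SAP 7.2.1 then says "Fit an Emax curve using nonlinear least squares approach. Estimate of the dose that reaches 90% concentration (with 95% CI) will be reported" and has no Adjustment row.

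The mixed model in SAP 7.3.2 covers milk thiamine at 4, 12 and 24 weeks, so it includes the primary outcome. Its Adjustment row reads "Health centre, human milk total thiamine at 2 weeks postnatal (linear mixed effects model only". The same limit appears in SAP 7.3.1 ("Health centre (linear regressions only") and SAP 7.3.4 ("Maternal ThDP at 2 weeks postpartum, health centre (linear regressions and mixed effects models only").

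The general rules allow this. SAP 5.6 says "Both unadjusted and adjusted analyses will be performed for some outcomes". Protocol section 11 applies "adjusted for randomization strata and levels at 2 weeks postnatal" to the comparisons between treatment groups, not to the dose-response curve. On missing data, SAP 5.3 says "Covariates pre-specified for adjustment in the analysis will be included in the imputation model", and imputation is done separately by treatment group.

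**The concern.** The trial exists to estimate one dose, and that estimate makes the least use of the baseline data. Milk is sampled at 2 weeks from every woman by design, and the SAP already treats the value as a useful covariate for this very outcome. Where adjusted and unadjusted analyses both exist, SAP 5.6 draws its conclusions from the adjusted one.

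As planned, 2-week milk can reach the primary estimate only by helping to impute missing 24-week values. For a woman whose 24-week value is observed, it explains none of the residual variation. If 2-week and 24-week milk thiamine are correlated, the interval for the primary dose is wider than the collected data require.

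**Working it through.** **Inputs.** SAP 3.6 gives 80 women per arm, 20% attrition (80 × 0.8 = 64 observed), SD 43 µg/L, minimum 136 and maximum 210 µg/L, with the 50% and 90% points at 1.2 and 2.4 mg/d. SAP 7.1 defines the target as the dose giving 90% of E0 + Emax. The correlation r is in neither document and is an assumption throughout.

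**1. The plan's own precision figure.** Emax = 210 − 136 = 74, and the target level is 0.9 × 210 = 189 µg/L, a fraction (189 − 136)/74 = 0.716 of Emax. The planning curve can be read in two ways:
- Reading A puts 189 µg/L at 2.4 mg/d: h = ln(0.716/0.284)/ln 2 = 1.34.
- Reading B puts 90% of Emax at 2.4 mg/d: h = ln 9/ln 2 = 3.17.

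Simulating unadjusted fits under reading A, with h fixed and 64 per arm, gives a 90% half-width of about 1.28 to 1.29 mg/d. This matches the stated ±1.29. The 95% half-width is about 1.5 to 1.6. The protocol calls ±1.29 a 90% interval and the SAP calls it a 95% interval. That is a separate matter, so only width ratios are used below.

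**2. Complete outcomes, equal r.** A linear baseline term changes each arm-mean variance from SD²/n to SD²(1 − r²)/n. All arms scale alike, so to first order the width for the dose scales by √(1 − r²), whether h is fixed or free.

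**3. 20% attrition, imputation by arm from 2-week milk, equal r.**
- Unadjusted: SD²[1/80 + (1 − r²)(1/64 − 1/80)].
- Adjusted: SD²(1 − r²)/64.
- Example at r = 0.5: 0.01250 + 0.75 × 0.003125 = 0.01484 against 0.75/64 = 0.01172, so the ratio is √(0.01172/0.01484) = 0.889.

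| r | ratio, complete outcomes | ratio, 20% attrition | simulated, reading A | simulated, reading B |
|---|---|---|---|---|
| 0.2 | 0.980 | 0.984 | 0.99 | 0.99 |
| 0.3 | 0.954 | 0.963 | 0.95 | 0.98 |
| 0.5 | 0.866 | 0.889 | 0.91 | 0.89 |

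The simulated columns (6,000 runs) have h fixed, 20% missing at random, imputation by arm and eight centres fitted with no true centre effect. At r = 0 the simulated ratio is 1.00 under both readings. Median dose estimates do not change.

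**4. Unequal r.** Suppose r is 0.5, 0.3, 0.2 and 0 at 0, 1.2, 2.4 and 10 mg. A common slope settles near the mean, b = (0.5 + 0.3 + 0.2 + 0)/4 = 0.25. Each arm-mean variance is then multiplied by 1 − 2br + b², which gives 0.8125, 0.9125, 0.9625 and 1.0625. The SE of the 10 mg mean rises by √1.0625 − 1 = 3%. Carried through the curve by the delta method with complete outcomes, the width ratio for the dose is 0.99 (A, h fixed or free), 0.98 (B, h fixed) and 1.01 (B, h free). A separate simulation of 1,200 runs, with Monte Carlo error of a few percent, gave 1.02 (A, fixed), 1.01 (B, fixed) and 1.07 (B, free). On both checks the gain is about nil.

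**5. With h free, as SAP 7.1 plans.** In 3,000 runs under reading A with equal r, the share of dose estimates above 10 mg/d moves from 24.8% to 24.5% at r = 0.3 and from 24.4% to 21.7% at r = 0.5. Under reading B it is below 1% with or without adjustment.

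**The case against.** The strongest reply is that this is a coherent design choice. The SAP confines adjustment to linear models in several places, so the omission looks deliberate: estimate the curve unadjusted, compare the groups adjusted. That stands, and it rules out calling the plan inconsistent. A reader might infer from SAP 7.3.2 or Protocol section 11 that the primary analysis breaks the plan's own adjustment rule, or that its estimate is biased. Neither follows. SAP 5.6 promises adjustment for some outcomes only, Protocol section 11 limits it to group comparisons, and dose is randomised.

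The second reply is that the gain rests on an unknown r, assumed equal across arms. This also stands. The SAP's own curve has a plateau, and if high doses bring women to a common ceiling, 2-week milk may predict little in those arms. Step 4 shows that the gain can then vanish, so a loss of precision cannot be stated as fact.

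Third, with h free and a curve like reading A, the instability of fitting four parameters to four doses outweighs anything a covariate can do. That is correct, and adjustment should not be presented as a remedy for it. Fourth, the health-centre terms have no demonstrated benefit here, which is why they are optional below.

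A reader might also suspect that the 2-week sample is taken after dosing starts, since Protocol 8.3 hands out the first capsules around the 2-week questionnaire. No passage states the order, but SAP 6.2 labels the 2-week data as baseline, so the documents do not support that suspicion.

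**Conclusion.** The point holds as a possible, inexpensive gain in precision for the primary estimate. It is not a question of validity. With r equal across arms, the interval for the dose would be about 2%, 5% and 13% narrower at r = 0.2, 0.3 and 0.5 with complete outcomes, and about 2%, 4% and 11% narrower after 20% attrition with imputation by arm. If r falls towards zero with dose, the gain is about nil. In that case, and at r = 0, the cost is negligible.

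These figures assume an additive linear baseline term with a common slope and, for the attrition case, 2-week milk observed in all women and outcomes missing at random. No half-width in mg/d is claimed, because that depends on how the planning curve is read. The change is worth making because it is cheap, with medium confidence that it will help.

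**What to change.** Add a row to SAP 7.2.1. Adjustment: human milk total thiamine at 2 weeks postnatal, centred at its sample mean, as an additive linear term. Centring matters because the target is 90% of E0 + Emax, so E0 must keep referring to the trial population. Health-centre indicators, centred at their sample proportions, may be added for consistency with SAP 5.6.

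Also state that:
- the full model is refitted in every bootstrap resample and every imputed dataset;
- the unadjusted curve is reported as a sensitivity analysis;
- if the adjusted model does not converge, the existing SAP 5.6 provision applies with one pre-specified step, which is to drop health centre first.

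It would help to state in the same place that the 2-week milk sample precedes the first capsule; the mixed model in SAP 7.3.2 relies on this too.

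The cost is a few sentences and no new data: one extra linear parameter, or eight with the seven centre terms, and some computation across the 100 resamples and 100 imputations.

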7.3 Secondary outcome variables

7.3.1 Infant thiamine diphosphate concentration (24 weeks)

Outcome:	Continuous outcome of infant thiamine diphosphate concentration (ThDP; nmol/L) at 24 weeks postpartum.
Primary analysis:	Fit an Emax curve using nonlinear least squares approach. Estimate of the dose that reaches 90% concentration (with 95% CI) will be reported.
Secondary analysis:	Fit an Emax curve using nonlinear least squares approach allowing curve to vary by presence/absence of genetic hemoglobin disorder. Estimates of the dose that reaches 90% concentration by genetic hemoglobin disorder status will be reported following evidence from the global test. Second, test for a linear relationship using linear regression with CRP at 24 weeks and treatment group as predictors. Estimate of the mean change (with 95% CI) in ThDP for one unit increase in CRP will be reported. Third, test for a linear relationship using linear regression with AGP at 24 weeks and treatment group as predictors. Estimate of the mean change (with 95% CI) in ThDP for one unit increase in AGP will be reported.
Adjustment:	Health centre (linear regressions only)

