9.8 Blood and human milk processing and analysis

Biological samples will be collected in the village (woman's home, or central village location such as the village chief's home), placed on ice, and transported to the field lab in Kampong Thom within 5 hours of collection. Phlebotomists will collect 9 mL venous blood from mothers and 5 mL from infants (in EDTA-coated Vacutainers). Venous blood samples will be processed as per **Figure 2**. All samples will be stored at -20°C for <1 week before being transported the National Institute for

Public Health Laboratory in Phnom Penh for storage at -80°C . Samples will be batch shipped on dry ice after the 24 weeks postnatal data collection is completed.

[figure not shown]

Figure 2: Processing protocol for venous blood and breast milk samples.

Venous blood samples will undergo analysis for both transketolase activity and thiamine diphosphate concentrations, as described in *3.3 Biomarkers of thiamine status*, by [name] at the NIHR BRC Nutritional Biomarker Laboratory at the University of Cambridge in the United Kingdom. At 2 weeks postnatal, maternal whole blood ThDP and erythrocyte transketolase activity will be measured. At 24 weeks postnatal, ThDP and transketolase activity will be measured in both whole blood and erythrocytes, and infant samples will be assayed for whole blood ThDP and erythrocyte transketolase activity. When ThDP is assessed in whole blood, concentrations must be normalized to hemoglobin concentrations and/or hematocrit (47). Therefore, hemoglobin concentration and hematocrit will be measured on all whole blood samples via a HemoCue 201 portable hemoglobinometer and capillary hematocrit tubes, respectively.

Evidence from the 2014 Cambodian National Micronutrient survey indicates that eThDP is affected by the presence/absence of genetic hemoglobin disorders. With this, it is vital to assess the presence/absence of genetic hemoglobin disorders, as this could influence participant's response to thiamine, it may influence transketolase, and it could change thiamine dosage requirements in other

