countries. Therefore, at one timepoint only (2 weeks postnatal for maternal, and 24 weeks postnatal for infant samples), an aliquot of 1 mL whole blood will undergo hemoglobin capillary electrophoresis analysis to identify structural hemoglobin variants (48) at the Pasteur Institute in Phnom Penh. Buffy coat samples will be stored in the BioBank in the Department of Applied Human Nutrition at Mount Saint Vincent University in Halifax, Nova Scotia, Canada, for potential later assessment of genetic hemoglobin disorders.

Biomarkers may be influenced by inflammation, which is common in this population (49,50). Plasma samples will be sent to [name] at the VitMin Lab in Germany for analysis of C-reactive protein (CRP) and α -1-acid-glycoprotein (AGP) using an immunosorbent assay (51). Note that this assay will also measure retinol binding protein (RBP), ferritin, and soluble transferrin receptor (sTfR). Other plasma samples will be stored in the BioBank for potential future use.

At 2, 4, 12, and 24 weeks postnatal, a full human milk expression will be collected (approx. 35 g) and approximate milk volume (weight of milk to 1 g) will be recorded. Samples will be mixed, and 2 mL aliquots obtained in amber cryovials (see **Figure 2**). Human milk thiamine concentrations will be measured by Drs. [name] and [name] at the USDA/ARS Western Human Nutrition Research Center, University of California, Davis (52).

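### The CRP and AGP models for ThDP leave out genetic hemoglobin disorder, a measured factor the plan elsewhere lets shift the ThDP level; adding it is a free, small improvement

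*Combined protocol and SAP*

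**What the plan says.** Protocol objective 16 (SAP secondary objective 6) asks what effect inflammation, measured by CRP and AGP, has on maternal and infant ThDP. Four models answer it.

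- **Infant, SAP 7.3.1.** The analysis is to "test for a linear relationship using linear regression with CRP at 24 weeks and treatment group as predictors". A separate model does the same for AGP. The adjustment line reads "Health centre (linear regressions only").
- **Maternal, SAP 7.3.4.** The analysis is a "linear mixed effects model with CRP at 2 and 24 weeks postnatal, time and treatment group as predictors", and again a separate one for AGP. The adjustment line reads "Maternal ThDP at 2 weeks postpartum, health centre (linear regressions and mixed effects models only").

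No hemoglobin-disorder term appears in any of them. Elsewhere the plan takes the variable seriously:

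- Protocol 9.8 says that national survey evidence "indicates that eThDP is affected by the presence/absence of genetic hemoglobin disorders", and it has hemoglobin typing done once per person: "2 weeks postnatal for maternal, and 24 weeks postnatal for infant samples".
- SAP 7.1 puts a hemoglobin-disorder coefficient on every Emax parameter, including E0, the level without supplementation. SAP 7.3.1 and 7.3.4 apply that model to infant and maternal ThDP.
- SAP 5.7 uses the variable only as a modifier of the treatment or dose effect.
- SAP 5.6 says that confounders for adjustment were chosen in advance and are listed by outcome in Section 7. It gives no reason for leaving this one out.

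**The concern.** Randomisation protects the treatment comparisons but not the CRP and AGP slopes. These are observational associations, and how they read depends on what else is in the model. If carriers of a hemoglobin disorder have different ThDP and also different CRP or AGP, a slope that ignores carrier status mixes the two. Objective 16 could then credit inflammation with a hemoglobin difference, or miss a real association. The reported 95% interval would not show it.

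The infant models are the more exposed. They have no earlier ThDP value to absorb a stable between-infant difference, whereas the maternal models adjust for 2-week ThDP.

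The plan is also uneven within one section. In SAP 7.3.1 the effect-modification Emax fit lets infant ThDP differ by hemoglobin disorder, and the next two analyses of the same outcome assume that it does not.

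**Working it through.** **Plan's own figure.** There is none for these models: no sample size, expected slope, effect of hemoglobin disorder or prevalence is given. From the documents come the 320 recruited and the 20% attrition allowance. Attrition is stated for the pairwise milk comparison, and applying it here is an assumption: 320 × 0.8 = 256 infants.

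**Assumed inputs (not in the documents).** Carrier proportion p = 0.3 or 0.5. Carriers' ThDP shifted by dY = 0.3 or 0.5 SD. Carriers' CRP or AGP shifted by dX = 0 (no link), or 0.1 to 0.5 (modest link). An SD here is the SD among people of the same carrier status.

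**Degrees of freedom.** The infant model has an intercept, the marker, 3 treatment terms and 7 centre terms, 12 in all. So df = 256 − 12 = 244 without the hemoglobin term and 243 with it.

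**Step 1: no link (dX = 0).** Bias is zero. The share of ThDP variance explained by carrier status is R² = dY²·p(1−p) / (1 + dY²·p(1−p)).

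- Low: 0.09 × 0.21 = 0.0189, and 0.0189/1.0189 = 0.019.
- High: 0.25 × 0.25 = 0.0625, and 0.0625/1.0625 = 0.059.

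The ratio of standard errors, with the term to without it, is √(1 − R²) × √(244/243). That is 0.993 at the low end and 0.972 at the high end, an interval about 1% to 3% narrower.

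**Step 2: modest link.** Bias in the slope (SD of ThDP per SD of marker) = dY·dX·p(1−p) / (1 + dX²·p(1−p)).

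- Low: 0.3 × 0.1 × 0.21 / (1 + 0.01 × 0.21) = 0.0063/1.0021 = 0.006.
- High: 0.5 × 0.5 × 0.25 / (1 + 0.25 × 0.25) = 0.0625/1.0625 = 0.059.

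The standard error of the unadjusted slope is √[residual variance / (marker variance × 244)].

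- Low: √[1.0189 / (1.0021 × 244)] = 0.065. Bias/SE = 0.0063/0.065 = 0.10.
- High: residual variance 1.0625 − 0.0588² × 1.0625 = 1.0588, so √[1.0588 / (1.0625 × 244)] = 0.064. Bias/SE = 0.0588/0.0639 = 0.92.

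So the bias is about 0.1 to 0.9 SE. If all 320 infants contributed (df 308), these ratios would grow by √(308/244) = 1.12.

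**Step 3: what 0.9 SE means.** With a true slope of zero, a two-sided 5% test shifted by 0.92 SE rejects with probability about Φ(−1.97 + 0.92) + Φ(−1.97 − 0.92) = 0.147 + 0.002, or roughly 15%. At 0.1 SE the rate stays close to 5%.

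**Step 4: cross-check by partial R².** Let R²y and R²d be the partial R² of hemoglobin disorder on ThDP and on the marker. Then bias/SE = √[R²y·R²d/(1 − R²d) × df]. At df 244, with rejection rates simulated over 4,000 runs at a true slope of zero:

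| R²y | R²d | Bias/SE | Rejection without term | Rejection with term |
|---|---|---|---|---|
| 0.05 | 0 | 0 | 5.1% | 4.8% |
| 0.05 | 0.01 | 0.35 | 6.1% | 4.9% |
| 0.10 | 0.02 | 0.71 | 10.9% | 4.8% |
| 0.20 | 0.05 | 1.60 | 36% | 4.5% |

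The last row assumes a far stronger effect on ThDP than Step 1 does. It shows how much the answer depends on the assumption and is not an expected size.

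**Step 5: precision when there is a link.** The ratio of standard errors becomes √[(1 − R²y)/(1 − R²d)] × √(244/243). With R²y = 0.02 and R²d = 0.05 it is 1.018, a slight loss. The gain in Step 1 therefore belongs to the no-link case and is not guaranteed.

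**The case against.** The strongest reply is that SAP 5.6 leaves the adjustment set to judgement, outcome by outcome, and that one more covariate in a low-priority observational analysis is a matter of taste. Several parts of that reply stand.

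- **The slopes are not shown to be confounded.** A reader might infer that they are. Confounding needs hemoglobin disorder to be related to CRP or AGP as well as to ThDP. The documents say that inflammation may influence biomarkers and nowhere tie it to hemoglobin status. The bias may be zero.
- **Hemoglobin disorder is not the only measured factor for ThDP.** A reader might infer that from its absence. Protocol 9.8 also says whole-blood ThDP has to be normalised to hemoglobin concentration and/or hematocrit, and both are measured. The SAP gives the outcome in nmol/L without saying whether it is normalised.
- **The cited evidence is for erythrocyte ThDP.** For infants, "infant samples will be assayed for whole blood ThDP and erythrocyte transketolase activity". The 2-week maternal ThDP is whole blood as well. Carrying the effect over is plausible, and the SAP itself does so when it tests hemoglobin disorder on infant ThDP, but it is an extrapolation.
- **A precision gain is small and not certain**, as Steps 1 and 5 show.
- **The maternal models have less to gain.** Adjusting for 2-week ThDP should absorb part of a stable genetic difference. As worded, 2-week ThDP also seems to be both a response and a covariate there, which should be clarified before any added term is interpreted.

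What does not stand is the idea that leaving the variable out is just as good. It is fixed genetically, so neither treatment nor inflammation can cause it, and adjusting cannot remove part of the effect being sought. It is already collected, and already used for the same outcomes.

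**Conclusion.** The point holds as a free improvement, not as an error in the plan. All four inflammation models omit a measured variable that the protocol says affects erythrocyte ThDP and that the SAP lets shift the ThDP level elsewhere.

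The size cannot be fixed from the documents. Under the assumed ranges, the omission costs about 1–3% of interval width if hemoglobin disorder is unrelated to CRP and AGP. It biases the infant slope by about 0.1 to 0.9 SE, at 256 infants, if there is a modest relation. The upper figure needs every assumed input at its maximum. In the maternal models the effect is expected to be smaller.

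A reader might go further and doubt the trial's main results. The documents do not support that: the primary dose estimate and the treatment comparisons do not use these models.

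**What to change.** Add genetic hemoglobin disorder (yes/no) as a main-effect covariate:

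- in the infant CRP and AGP models of SAP 7.3.1, using the infant's own status. This matters most, because no earlier ThDP is available;
- in the maternal CRP and AGP models of SAP 7.3.4, using the mother's status.

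SAP 5.6 and the opening of Section 7 describe adjustment variables as 2-week measurements, so add a sentence that infant status, although typed at 24 weeks, is fixed from conception and is treated as a baseline variable. Under SAP 5.3, naming it as a covariate also brings it into the imputation model.

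In the same edit, state how whole-blood ThDP is normalised, and whether 2-week maternal ThDP is a response or a covariate in the mixed models. If the variable is left out on purpose, give the reason.

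The cost is a few lines of SAP text and one degree of freedom per model. No new measurement is needed.
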